Compare IVUS with angiography ographic Guidance PCI
Long-term clinical efficacy of acute STEMI

Appisor: The Second Affiliated Hospital
of Zhejiang University Medical
College

Principal investigator (PI): [name]

Key participants: [name], [name], [name]

Center Laboratory: The Second Affiliated Hospital
of Zhejiang University Medical
College

Version Number: Version 1.0

Version Date: April 15th, 2020

Investigator's signature: _____

Directents

COVERFOR.....	1
DIRECTORY.....	2
SCHEMESUMMARY.....	4
RESEARCH FLOWCHART.....	7
1、 RESEARCH	
BACKGROUND.....	8
2、 RESEARCH	
PURPOSE:.....	8
3、 STUDY	
ENDPOINT:.....	8
3.1MAINENDPOINT	8
3.2SECONDARYENDPOINT	8
4、 RESEARCH AND DESIGN.....	8
5、 SUBJECT SELECT.....	9
5.1INCLUSION CRITERIA	9
5.2 ELIMINATION CRITERIA	9
6、 RESEARCH METHODS.....	10
6.1 TREATMENT ALLOCATION METHOD OF SUBJECTS	10
6.2 VISIT PLAN	10
6.3 THE DATA COLLECTION PLAN.....	11
6.4 DRUG TREATMENT	15
6.5 INTRAVASCULAR ULTRASOUND EXAMINATION	15
7、 DATA MANAGEMENT.....	15
7.1 DATA RECORDS.....	16
8、 ETHICS AND REGULATORY REQUIREMENTS.....	16
8.1 ETHICAL CONSIDERATIONS.....	16

8.2. ETHICS REVIEW.....	16
8.3 INFORMED CONSENT FORM.....	16
8.4 REVISION PLAN.....	17
8.5 SCHEME DEVIATION UNDER EMERGENCY CONDITIONS.....	17
9、RESEARCH MANAGEMENT	
9.1 PROGRAMME COMPLIANCE.....	17
9.2 SCHEME MODIFICATION.....	17
10、DATA	
MANAGEMENT.....	17
10.1 DATA COLLECTION AND PROCESSING.....	17
10.2 DATA QUALITY ASSURANCE.....	17
10.3 RAW DATA MANAGEMENT.....	18
10.4 DEFLECTION AND SYSTEM ERROR CONTROL.....	18
11、STATISTICAL ANALYSIS OF.....	18
11.1 STATISTICAL SOFTWARE.....	18
11.2 STATISTICAL METHODS.....	18
11.3 SAMPLE SIZE CALCULATION.....	19
12、RESULTS RELEASED.....	19

Scheme Summary

Clinical ison of Intravascular Ultrasound (IVUS) Guided and Angiography (angiographie) for PCI Acute ST Section Elevated Myocardial infarction (STEMI)

Research Objective	Comparing the long-term clinical efficacy of IVUS-guided and angiography-guided PCI in patients with acute STEMI
Test device	IVUS (Opticross™ catheter)
Control device	NA
Research and Design	Prospective, randomized, and multi-center observational trials
Number of planned subjects	200 Cases
Planned number of locations	Ten clinical sites
Main endpoint	The primary endpoint was major cardiac adverse events (MACE), defined as cardiac death, recurrent myocardial infarction (MI, q and non-q waves), and target vasascularization (TVR) at 12 months.
Secondary endpoint	
The following indicators will be evaluated annually for 3 years.
 
• MACE(2-3 assessed annually)• Target lesion blood revascularization (TLR)• Target lesion failure (TLF)• Target vascular revascularization (TVR)• Target blood vessel failure (TVF)• Myocardial infarction (Q waves and non-Q waves)• Cardiac death• Noncardiac death• All-cause of death (cardiac and noncardiac)

	
 • In-stent thrombosis (ARC classification: determining / possible intrastent thrombosis)
Subsequent arrangements	Clinical follow-up for 30 days, 6 months, 12 months, 24 months, 36 months
Study duration	At 36 months, the
Antiplatelet therapy	Guidance according to current guide
Clinical inclusion criteria	
 • C1. Age > 18 • C2. STEMI Attack > 30 min, but < 12 h • ST segment elevation of at least 2 consecutive guided ≥ 1 mm or new LBBB on the C3. ECG • C4. is willing and able to provide informed consent form
Angiographic inclusion criteria	
The AI1. has at least one coronary artery associated with the infarction, in which the
 
 • Criminal lesion and suitable for stent placement • The reference diameter of criminal vessels is ≥ 2.5 mm but ≤ 4 mm • TIMI blood flow score ≤ 1 in the criminal lesion segment before guiding the lead to pass 
AI2. does not have excessive twists and calcification in criminal lesion segments that allow stents

Clinical Exclusion Standards	
Patients with CE1. have contraindications to the drugs to be used during the study
 
CE2. cardiogenic shock associated with hemodynamic instability
 
CE3. has bleeding or known coagulation disease
 
CE4. has a history of cerebrovascular accident (CVA) or transient ischemic attack (TIA) in the past 6 months, or intracranial tumor, aneurysm or arteriovenous malformation; or active peptic ulcer or active gastrointestinal (GI) bleeding in the past 2 months; or

	
scheduled major surgery within 6 weeks; or known platelet count <100,000 / mm³Or Hb <10g/dL
 
Planned CE5. surgery that cause deactivation of ADP receptor antagonist
 
Other serious CE6. diseases such as cancer may reduce life expectancy to below 1 year
 
CE7. recurrent myocardial infarction within 7 days after acute myocardial infarction

Contrast exclusion criteria	
The AE1. bifurcation lesion does not identify it as a criminal lesion
 
The AE2. criminal lesion is located in the left aorta
 
AE3. diffuse lesions associated with unidentifiable criminal lesions
 
AE4. or stent implantation due to stent thrombosis
 
AE5. may plan CABG bypass surgery within 30 days
 
AE6. patients develop renal failure during dialysis

Statistical Methods	
Major statistical assumptions	The IVUS guidance group may have better results than the angiography guidance, especially in TVR or TLR.
Statistical analysis	
Descriptive statistics (e. g., mean, standard deviation, n, minimum, maximum), or median (95% CI) (continuous variable), or frequency tables (classification variables), are used to summarize their demographic characteristics, clinical history, laboratory examination, and risk factors.
 
We will use Logistic regression to analyze the correlation of plaque morphology with clinical results both 12 and 36 months after STEMI.

Sample parameter size	To support the objectives, the sample size of this test will be at least 200 subjects.
Core Laboratory	Core Laboratory data Analysis

1. Research Background

Intravascular ultrasound (IVUS) has been increasingly used for selective and emergency percutaneous coronary intervention. Recent randomized controlled studies, large-scale registration studies, and meta-analysis have demonstrated significant advantages in reducing mortality, myocardial infarction, and target revascularization compared with separate angiographic-guided angiography.

As shown in previous studies [1-5], fewer clinical results on clinical studies of IVUS guided PCI in acute myocardial infarction (AMI) exist and the results remain controversial. This study will explore the effects of IVUS-guided PCI on clinical outcomes in patients with acute ST-segment elevation myocardial infarction (STEMI).

2. Research Objective

Comparing the long-term clinical efficacy of IVUS and angiography-guided PCI in dealing with acute STEMI.

3. study endpoint

.13. Main endpoint

The primary endpoint was major cardiac adverse events (MACE), defined as cardiac death at 12 months, recurrent myocardial infarction (MI, Q and non-Q waves), and target vascular revascularization (TVR).

.23. Secondary endpoint

The following indicators will be evaluated annually for 3 years.

- MACE(2-3 assessed annually)

- Target lesion blood revascularization (TLR)
- Target lesion failure (TLF)
- Target vascular revascularization (TVR)
- Target blood vessel failure (TVF)
- Myocardial infarction (Q waves and non-Q waves)
- Cardiac death
- Noncardiac death
- All-cause of death (cardiac and noncardiac)
- In-stent thrombosis (ARC classification: determining / possible intrastent thrombosis)

4. Research and Design

This study is a prospective, single-center, randomized controlled trial to be conducted at the Second Affiliated Hospital of Zhejiang University School of Medicine, with plans to recruit 200 STEMI subjects.

Subjects were randomly assigned to 2 treatment groups in a 1: 1 ratio.

5. Subject Selection

Ten centers plan to include 200 male and female patients over 18 to treat subjects according to the Intervention Guidelines of the American Heart Association and the American College of Heart Disease.

The number of subjects recruited each center does not exceed 40% of the total planned enrollment.

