6.2 Visit Plan

The study visits included subject visits during hospitalization (Visit 1), during which the subjects were enrolled and randomized for subsequent treatment. All subjects randomized to trial treatment will be part of the safety set and will receive clinical evaluation on days 30, 6, 12, 2 and 3 years after the surgery. Follow-up requires the collection of data required by the protocol, including accompanying medication, recording any adverse events and collecting original documents.

The number of visits and duration of the subject may be treated depending on:

- (a) When patients are included in the study;
- (b) When a clear or possible injury occurs, a decision needs to terminate the study early;
- (C) End the study.

Subject follow-up Program:

- Visit 1 inpatient visit;
- Follow-up for 30 days after Visit 2 surgery;

- Follow-up for 6 months after Visit 3 surgery;
- Follow-up for 12 months after Visit 4 surgery;
- Follow-up for 2 years after Visit 5 surgery;
- Follow-up for 3 years after Visit 6 surgery;

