- Current antiplatelet drugs. Information on dose changes, interruptions, and cessation of medication must be recorded.

12 months after Visit4 ()

All subjects in the group must receive an angiography evaluation at 12 months after stenting.

- Photoast Data
- Adverse events and endpoint-related events to evaluate and collect the original documents.
- In addition, the researchers will decide which antiplatelet drugs patients should receive at the end of their research treatment as part of their ongoing clinical treatment, and this transition information will be recorded.
- NYHA cardiac function rating
- Under treatment principles, if the patient did not terminate participation in the study, the 12 months or at the end of the follow-up plan to record the end point or serious adverse events.

2 years after Visit 5()

All subjects in the group must be evaluated 2 years after stenting. Follow-up assessments can be conducted either by telephone or at the research center. The following assessment must be completed at 6 months of postoperative follow-up.

- Adverse events and endpoint-related events to evaluate and collect the original documents.
- Current antiplatelet drugs. Information on dose changes, interruptions, and cessation of medication must be recorded.

Visit 6(, 3 years after surgery)

All subjects in the group must be evaluated 3 years after stenting. Follow-up assessments can be conducted either by telephone or at the research center. The following assessment must be completed at 6 months of postoperative follow-up.

- Adverse events and endpoint-related events to evaluate and collect the original documents.
- Current antiplatelet drugs. Information on dose changes, interruptions, and cessation of medication must be recorded.

Unanticipated follow-up

Additional visits for subject safety, drug dose adjustment and need to be recorded in the case report table.

Lost visit

Patients who do not follow-up by protocol and revoke informed consent will repeatedly attempt to contact and determine their life status, the occurrence of any type of myocardial infarction or stroke. If the subject misses any 2 consecutive follow-up and fails to contact (i. e. 2 phone calls, later approved letters), the subject will be deemed missed.

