11.2 Statistical Methods

Statistical description is given below:

Continuous variables: number of group description examples, number of missing cases, average, median, standard difference, quartile range, minimum, and maximum.

Classification variable: Number of missing cases, number of splitting frequencies, and percentage of the group description.

Statistical tests: All statistical tests are bilateral tests, and P values less than or equal to 0.05 will be considered to be of statistical significance. (Unless specifically specified).

Overview of statistical methods: different analysis methods will be adopted according to the classification of groups and data characteristics, see the statistical analysis plan for details. The main statistical analysis methods include t test, card square test, Fisher accurate probability method, ANOVA, covariance, Logistic regression, CMH card square and rank and test methods to compare the differences among different groups.

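### Section 11.2 lists no time-to-event method for endpoints followed to 36 months, and the tracing of lost patients omits TVR, a component of the primary endpoint

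*Combined protocol and SAP*

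**What the plan says.** Section 3 makes 12-month MACE (cardiac death, recurrent MI, TVR) the primary endpoint. For the secondary endpoints, which include MACE in years 2 and 3, TVR, TLR, MI and the death categories, it says: "The following indicators will be evaluated annually for 3 years".

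On analysis, section 11.2 sets two-sided tests at 0.05 and states that "different analysis methods will be adopted according to the classification of groups and data characteristics, see the statistical analysis plan for details". Its list of main methods opens with the t test, chi-square, Fisher's exact test and ANOVA, and continues with "covariance, Logistic regression, CMH card square and rank and test methods to compare the differences among different groups". No method is assigned to an endpoint, and no time-to-event method appears. The Scheme Summary adds one outcome model: "We will use Logistic regression to analyze the correlation of plaque morphology with clinical results both 12 and 36 months after STEMI".

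On incomplete follow-up, section 6.3 (Lost visit) says that staff "will repeatedly attempt to contact and determine their life status, the occurrence of any type of myocardial infarction or stroke". TVR is not named there. The Scheme Summary states the hypothesis as "The IVUS guidance group may have better results than the angiography guidance, especially in TVR or TLR". Section 10.2 targets follow-up above 95%.

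The only analysis set named is in section 6.2: "All subjects randomized to trial treatment will be part of the safety set". A garbled line under the 12-month visit in section 6.3 may refer to intention-to-treat.

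**The concern.** Over 36 months some patients will be lost and some will die of noncardiac causes, which lie outside MACE. A chi-square test or logistic regression at a fixed time must class each such patient as event-free or drop them. The supplied text gives no rule, and the arm difference depends on the rule, more so if loss differs between arms. A time-to-event analysis uses each patient's follow-up up to loss and needs no such classification, provided loss is unrelated to risk.

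The tracing rule is a separate gap, at data collection. A patient traced as alive without MI could be recorded as MACE-free although nobody asked about revascularisation. That would under-count a component of the primary endpoint, and one of the two outcomes (TVR, TLR) in which benefit is expected. No analysis method can recover an event that was never sought.

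**Working it through.** **Inputs.** From the documents: 200 patients at 1:1, so 100 per arm; follow-up target above 95% (10.2). The documents give no event rates, and section 11.3 says no sample size calculation was made, so there is no stated figure to reproduce. Assumed: 36-month MACE 20% control v 10% IVUS; noncardiac death 6% per arm; loss 5% or 15%, unrelated to risk.

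**Step 1. True difference.** Convert each risk p to a cumulative hazard H = −ln(1 − p): MACE 0.2231 (control) and 0.1054 (IVUS), noncardiac death 0.0619, loss 0.0513 (5%) or 0.1625 (15%). With constant hazards, cumulative incidence without loss is H_M/(H_M + H_D) × (1 − exp(−(H_M + H_D))).
- Control: 0.2231/0.2850 × (1 − 0.752) = 19.42%
- IVUS: 0.1054/0.1672 × (1 − 0.846) = 9.70%
- Difference: 9.71 points (differences here and below are taken before rounding)

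**Step 2. Fixed-time handling.** With H the sum of all three hazards, the proportion with each first outcome is H_k/H × (1 − exp(−H)). At 5% loss, control has MACE 18.95%, noncardiac death 5.25%, lost 4.36%; IVUS has 9.46%, 5.56%, 4.61%. Fewer than 5% are then lost before an event, which is within the target. Three possible rules:
- (a) lost count as event-free: 18.95 − 9.46 = 9.49
- (b) lost dropped, E/(1 − L): 19.81 − 9.92 = 9.89
- (c) lost and noncardiac deaths dropped, E/(1 − L − D): 20.96 − 10.54 = 10.43

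| Loss, control / IVUS | (a) | (b) | (c) | Cumulative incidence, simulated mean |
|---|---|---|---|---|
| 5% / 5% | 9.49 | 9.89 | 10.43 | 9.74 |
| 15% / 15% | 9.01 | 10.28 | 10.87 | 9.71 |
| 15% / 5% | 8.53 | 10.78 | 11.43 | 9.75 |
| 5% / 15% | 9.97 | 9.40 | 9.87 | 9.71 |

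The last column comes from 60,000 simulated trials per setting.

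**Step 3. Scale.** The 95% CI half-width is 1.96 × √(0.1942 × 0.8058/100 + 0.0970 × 0.9030/100) = 9.7 points. The largest shift, 11.43 − 9.71 = 1.72, is 0.18 of that. With equal 5% loss, simulated power is 49% for both the binary tests and log-rank. With 15% v 5% loss it is 42.9% to 54.5% depending on the rule, against 49.0% for log-rank. With equal MACE of 20% and 15% v 5% loss, the rules give false differences of −0.96, +0.89 and +1.00 points, and type I error of 5.4% to 5.6% against 5.0%.

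**Step 4. TVR not sought after loss.** If later TVR is never sought and the patient counts as TVR-free, that is rule (a) applied to TVR. Assuming 36-month TVR of 12% v 6% and any death 10%, the true difference is 5.70 points. Rule (a) gives 5.57 with 5% loss in both arms and 5.00 with 15% v 5%.

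**Step 5. The 12-month endpoint.** Assuming MACE 10% v 5%, noncardiac death 1% and 5% loss, the three rules give 4.85, 5.09 and 5.14 against a true 4.98, with a CI half-width of 7.3, so handling matters little. The choice of test can matter more. With 10 v 3 events per 100, Pearson chi-square is 200 × (10 × 97 − 3 × 90)²/(100 × 100 × 13 × 187) = 4.03, p = 0.045; Fisher's exact p = 0.082. Section 11.2 lists both tests, and they fall on opposite sides of 0.05.

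**The case against.** The strongest reply is that section 11.2 calls its list the main methods, does not present it as complete, and points to a separate plan. Time-to-event methods and the 12-month test may be specified there. This stands, and it limits the point to the supplied text.

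Second, the primary endpoint is binary at a fixed time in two arms, and section 11.2 lists valid tests for it. A reader might infer that the trial has no usable primary analysis, or that the plaque-morphology model is the planned arm comparison. The documents support neither. What is missing is the choice among listed tests, and the plaque model addresses a different question.

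Third, the 36-month shifts are small at the target follow-up. Among the three rules, only the one that drops noncardiac deaths exceeds 9.9 points with 5% loss in each arm, and no document proposes it. The larger shifts need 15% loss in one arm. Cumulative incidence stays near 9.7 because the calculation assumes loss unrelated to risk; informative loss would bias time-to-event methods too. All of this stands.

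Fourth, section 6.3 records endpoint events at every scheduled visit, so the tracing gap affects only patients who miss visits. As worded, that clause also covers people who revoke consent, which limits what may be sought. This stands as well. It narrows the gap but does not explain why TVR is left out.

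**Conclusion.** The point holds as a low-cost improvement in two places. The group-comparison methods in the supplied text include none suited to dated events over 36 months, and the tracing rule omits a component of the primary endpoint.

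With balanced loss inside the follow-up target, the arm difference moves by less than one point (9.5 to 10.4 against 9.7). It moves by up to 1.7 points in the 15% v 5% stress case, still well inside the CI half-width of 9.7. A reader might infer that the 36-month results would be seriously biased or the type I error materially inflated; these figures do not support that. They rest on assumed event and loss rates, constant hazards and loss unrelated to risk. The omission of TVR from tracing is a matter of text and needs none of these assumptions; its numerical effect does.

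**What to change.** 1. In section 11.2, analyse MACE and the other secondary endpoints to 36 months in all randomised patients by assigned arm, as time from randomisation to first event. Censor at the last contact at which every component of the endpoint was ascertained. Report cumulative incidence with deaths outside the endpoint as a competing event, and a cause-specific Cox hazard ratio with 95% CI.
2. In section 6.3 (Lost visit), add TVR, asked as any repeat revascularisation, to the outcomes sought for patients who miss visits, within the limits of their consent.
3. In the same edit, name one 12-month MACE analysis by assigned arm: the risk difference with a score 95% CI and the matching Pearson chi-square test. State how lost patients are handled. Do not make counting them as event-free the sole rule, since that is biased when loss differs by arm. Report the 12-month cumulative incidence difference as a sensitivity analysis.

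If the separate statistical analysis plan already contains items 1 and 3, aligning section 11.2 with it is enough.

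**Cost.** A few lines of text and routine code. Event and last-contact dates must be confirmed in the CRF; source documents for events are already required, so event dates are probably recoverable. Time-to-event methods add no power when loss is equal.

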5.1 Inclusion criteria

The 200 subjects who met the inclusion / exclusion criteria will undergo emergency angiography and the following

Clinical inclusion criteria

- C1. Age > 18
- C2. STEMI Attack > 30 min, but < 12 h
- ST segment elevation of at least 2 consecutive guided ≥ 1 mm or new LBBB on the C3. ECG

- C4. is willing and able to provide informed consent form

Angiographic inclusion criteria

The AI1. has at least one coronary artery associated with the infarction, in which the

- Criminal lesion and suitable for stent placement
- The reference diameter of criminal vessels is ≥ 2.5 mm but ≤ 4 mm
- TIMI blood flow score ≤ 1 in the criminal lesion segment before guiding the lead through

AI2. does not have excessive twists and calcification in criminal lesion segments that allow stents

5.2 Elimination criteria

Clinical Exclusion Standards

Patients with CE1. have contraindications to the drugs to be used during the study

CE2. cardiogenic shock associated with hemodynamic instability

CE3. has bleeding or known coagulation disease

CE4. has a history of cerebrovascular accident (CVA) or transient ischemic attack (TIA) over the past 6 months, or intracranial tumor, aneurysm or arteriovenous malformation; or active peptic ulcer or active gastrointestinal (GI) bleeding in the past 2 months; or scheduled major surgery within 6 weeks; or known platelet count $<100,000 / \text{mm}^3$ Or Hb $<10\text{g/dL}$

Planned CE5. surgery that cause deactivation of ADP receptor antagonist

Other serious CE6. diseases such as cancer may reduce life expectancy to below 1 year

CE7. recurrent myocardial infarction within 7 days after acute myocardial infarction

Contrast exclusion criteria

The AE1. bifurcation lesion does not identify it as a criminal lesion

The AE2. criminal lesion is located in the left aorta

AE3. diffuse lesions associated with unidentifiable criminal lesions

AE4. or stent implantation due to stent thrombosis

AE5. may plan CABG bypass surgery within 30 days

AE6. patients develop renal failure during dialysis

6. Research Methods

6.1 Treatment allocation method of subjects

Once the subject has signed a research informed Consent (ICF) approved by the Ethics Committee (EC), meets all clinical and contrast inclusion criteria and does not meet the clinical or contrast exclusion criteria, the subject is considered qualified and may participate in this test. Qualified subjects were randomized to 1 of the two treatment groups at 1: 1: test groups (IVUS guidance group) or control groups (contrast guidance group).

